12.0 EFFECTIVENESS OF ANALYSIS

Quantitative, but not statistically powered, trend-analysis of effectiveness of active treatment vs. sham.

Comparison of mean magnitude of treatment effect (change in NPRS) between sham and active treatment (cumulative responder analysis)

Medication usage

Non-drug treatment

Global Pain Scale (GPS)

Patient satisfaction with treatment

Presence of unwanted treatment effects, including paresthesia, irritation or discomfort, referred pain, and motor effects.

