11.0 DEFINITION OF SUCCESS

Treatment success is a 30% reduction in mean baseline pain score on the 0 to 10 Numeric Pain Rating Scale (NPRS) that persists at least 1 hour and occurs at any time in the period from treatment through 48-hour follow-up.

Study success is at least 3 of 10 treatment patients meeting the criteria for treatment success and no serious adverse events reported in any subject related to active treatment.

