16.0 SAMPLE SIZE

20 (10 control and 10 intervention) subjects who complete treatment/sham based on an estimate that this number will be sufficient to reveal whether this therapy is safe and whether further studies are warranted to investigate the level of any clinically meaningful pain relief.

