26.0 DATA ANALYSIS

Descriptive statistics, trend analysis of endpoint means for effectiveness. Tabular collection of adverse events with narrative

STUDY SCHEDULE AND DESCRIPTION OF DATA COLLECTION

Time of data collection	Data collected						
	Log entry	Demographics	History	Informed consent	NPRS first rating or since last rating given	AE	Additional endpoints
*Eligibility screened and offered participation	X	X	X	X			
*Pain each day in 7-day period					X	X	
Day 1 (baseline = start of treatment)					X	X	X
During treatment: 5 minutes					X	X	
10 minutes					X	X	
After treatment: 1 hour					X	X	
2 hours					X	X	
3 hours					X	X	
4 hours					X	X	
8 hours					X	X	
12 hours					X	X	
24 hours					X	X	
48 hours					X	X	
72 hours					X	X	
*Final assessment 7 & 30 days (+3)		X (employment status only)			X	X	X

*Data can be collected in person, via mail, via telephone, email, or fax

LAY SUMMARY

The study will evaluate whether an experimental medical device that emits a brief, intense magnetic field will relieve pain in the low back. The United States Food and Drug Administration (FDA) has approved a similar device for treatment of migraine, but this type of device has not been studied for the treatment of low back pain. No significant adverse reactions or side effects have been reported from the use of magnetic stimulation for headache treatment. Some patients who have migraine headaches have excellent pain relief with the magnetic treatment even if they did not get pain relief with medications.

We do not know whether magnetic treatment will relieve low back pain, so we will test this by applying a powerful electromagnet to the painful area of the low back. In some subjects, the magnet will be turned on, but in other patients the magnet will not be turned on. Neither subjects nor subjects' treating doctor will know whether the magnet was turned on or not, although the study team will know which subjects received treatment with magnetic pulses. The effect on pain will be recorded periodically for 2 days. If the subjects' reported pain is reduced as a result of the magnetic treatment compared with subjects who did not have the magnet turned on, then the magnet might have reduced the pain. Additional studies will be needed to further investigate whether this therapy reduces low back pain.

Keywords: **low back pain, TCMS (Transcutaneous Magnetic Stimulation), TENS (Transcutaneous Electrical Nerve Stimulation)**

RATIONALE AND BACKGROUND

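### The active-versus-sham comparison is an undefined trend in means with no interval, and the only numerical success rule ignores the sham arm, yet Section 16 says 20 subjects will suffice to show whether further studies are warranted

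*Combined protocol and SAP*

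**What the plan says.** Section 12 describes the comparison with sham as a "Quantitative, but not statistically powered, trend-analysis of effectiveness of active treatment vs. sham". It then lists a comparison of mean NPRS change between the arms, with a cumulative responder analysis mentioned in brackets, followed by several secondary items. Section 26 gives the whole statistical method for effectiveness as "Descriptive statistics, trend analysis of endpoint means for effectiveness". Neither section names an interval, a test, a margin or an NPRS time point, and neither defines a trend.

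Section 11 does contain a numerical rule: "Study success is at least 3 of 10 treatment patients meeting the criteria for treatment success", together with no serious adverse event related to active treatment. A responder needs a 30% reduction from mean baseline NPRS that lasts at least 1 hour and occurs at any time from treatment through 48 hours. The sham arm does not enter the rule.

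Section 16 sets the size at "20 (10 control and 10 intervention) subjects who complete treatment/sham" and justifies it by an estimate that "this number will be sufficient to reveal whether this therapy is safe and whether further studies are warranted". It gives no SD, target difference, response rate, alpha or power.

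**The concern.** The trial randomises half its subjects to a sham device so that non-specific improvement can be told apart from an effect of the magnet. That contrast is the part of the analysis left undefined. A difference in two means of 10 subjects each, reported without an interval, does not show the reader how far it could have arisen by chance. A favourable difference may be noise, and an unfavourable one may hide a real benefit.

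Section 11 does not fill the gap. Three responders in the active arm satisfy its efficacy part whether the sham arm has none, three or ten.

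What is at stake is the conclusion claimed in Section 16. If the trial is to inform a decision on further study, its report must show what the data can and cannot exclude about active against sham. The plan does not provide for this.

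**Working it through.** **Inputs from the document.** n = 10 per arm (Section 16); the contrast is the difference in mean NPRS change (Section 12); the success threshold is 3 of 10 active responders (Section 11).

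**Inputs assumed, because the document gives none.** SD of NPRS change 1.5, 2, 2.5 or 3 points; non-specific responder rate 10% to 50%; illustrative responder counts of 3/10 active and 1/10 sham.

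**The plan's own figure.** The 20 subjects cannot be reproduced, since Section 16 offers only an estimate with no statistical inputs.

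**Step 1: precision of the mean difference.** Half-width = t(0.975, 18 df) × SD × √(2/10) = 2.101 × 0.4472 × SD = 0.940 × SD.

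| Assumed SD (points) | Standard error | 95% half-width (points) |
|---|---|---|
| 1.5 | 0.671 | 1.41 |
| 2.0 | 0.894 | 1.88 |
| 2.5 | 1.118 | 2.35 |
| 3.0 | 1.342 | 2.82 |

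At SD 2, an observed advantage of 1 point would have an interval from 1 - 1.88 = -0.88 to 1 + 1.88 = 2.88 points. That covers both no effect and a benefit of nearly 3 points.

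**Step 2: how often noise alone looks favourable.** With no true effect and no bias, the chance of an observed advantage of at least 1 point is P(Z > 1/SE). This is 6.8%, 13.2%, 18.6% and 22.8% for the four SDs.

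**Step 3: precision of the responder difference.** Take 3/10 against 1/10, a difference of 0.20. The Wilson 95% limits are 0.108 to 0.603 for 3/10 and 0.018 to 0.404 for 1/10. Newcombe's limits are:

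- lower: 0.20 - √[(0.300 - 0.108)² + (0.404 - 0.100)²] = 0.20 - 0.36 = -0.16
- upper: 0.20 + √[(0.603 - 0.300)² + (0.100 - 0.018)²] = 0.20 + 0.31 = +0.51

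The active arm here meets the Section 11 threshold, yet the comparison with sham runs from 16 points worse to 51 points better.

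**Step 4: what the Section 11 rule can carry without sham.** If the device is inert and each active subject responds non-specifically with probability p, the efficacy part is met with probability P(X ≥ 3), X ~ Binomial(10, p).

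| Assumed p | P(at least 3 of 10) |
|---|---|
| 10% | 7.0% |
| 20% | 32.2% |
| 30% | 61.7% |
| 40% | 83.3% |
| 50% | 94.5% |

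The meaning of a pass depends almost entirely on the non-specific response rate. The sham arm estimates that rate, and the rule does not use it.

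**The case against.** The strongest defence is that the trial calls itself preliminary in Sections 1 and 2 and says in Section 12 that it is not powered. Descriptive reporting is a legitimate, disclosed choice for a pilot, and lack of power is not an error here. That stands. It does not answer the point, because an interval requires no power, and Section 16 goes beyond description when it claims sufficiency for a conclusion about further studies.

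A second defence is that Section 12 refers to the magnitude of the effect and to a cumulative responder analysis, so the plan looks at more than arm means. This also stands in part. But the responder analysis appears only in brackets after a comparison of means, with no interval or threshold.

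A reader might infer something stronger: that effectiveness will be judged by the sign of the difference, so that an inert device succeeds half the time. The document does not support this. Section 11 sets a numerical success rule, and no section makes the direction of the difference the basis for going forward. Nor does any section say whether the Section 11 rule or the Section 12 trend settles whether further studies are warranted. The one-half figure follows from symmetry and would hold for any equal arm sizes, so it says nothing about 10 per arm. The lay summary says only that the magnet might have reduced the pain if active does better than sham, and adds that more studies will be needed. That is cautious lay text and not an analysis rule.

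**Conclusion.** The concern holds in a limited form. The only planned effectiveness comparison with sham is descriptive, its trend is undefined and has no interval, and the one numerical criterion leaves sham out. Against that, Section 16's unqualified claim of sufficiency is not supported.

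The imprecision is large: ±0.94 SD for the mean difference, or 1.41 to 2.82 NPRS points over the assumed SDs, and about -16 to +51 percentage points for an illustrative 3/10 against 1/10. The 0.94 multiplier depends only on 10 analysed subjects per arm and a common SD. The values in points, the responder counts and the non-specific response rates are assumptions. All the figures assume no bias between arms, whereas the trial is single-blind and the lay summary says the study team will know the allocation. An interval would not capture such bias.

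This should be corrected, but it does not invalidate the trial as a pilot.

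**What to change.** In Sections 12 and 26, replace the trend analysis with estimation, using data already collected:

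- the active-minus-sham difference in mean NPRS change from baseline at one time point named in advance, with a two-sided 95% t interval. The times common to Section 9.4, the schedule of events and the data-collection table are 1, 2, 4, 8, 12, 24, 48 and 72 hours;
- the difference between arms in the proportion meeting the Section 11 responder definition, with a two-sided 95% Newcombe interval.

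In Section 16, replace the sufficiency claim with the expected precision, about ±0.94 SD for the mean difference at 10 per arm. Report the Section 11 result beside the sham responder rate and the interval for the difference.

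The interval should not become a rule to proceed whenever it still includes a worthwhile benefit. In simulation at SD 2, an inert device would meet such a rule in about 82% of trials for a 1-point benefit and 44% for a 2-point benefit.

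The cost is revised wording and minutes of analysis, with no extra subjects, visits or measurements. The drawback is that the trial's stated ability becomes less favourable.

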9.0 ASSESSMENTS

9.1 Numeric Pain Rating Scale (NPRS):

0 to 10 numerical pain rating scale with equally spaced numerical intervals ranging from 0 representing “no pain” to 10 representing the “worst imaginable pain”

9.2 Baseline severity (Pain Diary):

Patient will document in a diary the severity of their pain on each day of the preceding week just prior to treatment.

9.3 Severity during treatment (immediate benefit):

At 5- and 10-minutes

9.4 Severity after treatment is completed (treatment durability):

1, 2, 4, 8, 12, 24, 48 and 72 hours post-treatment.

9.5 We will also follow-up with patients at 7and 30 days post-treatment,

Data collected at baseline, 7 day and 30 day follow-up:

Global Pain Scale (GPS)

Medication usage -Case Report Form

Non-drug treatment -Case Report Form
Functional Status (ADLs, Mobility, Employment)- Case Report Form

Patient satisfaction with treatment- Case Report Form

Presence of unwanted treatment effects, including paresthesia, irritation or discomfort, referred pain, and motor effects. – Case Report Form

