17.0 RECRUITMENT, ENROLLMENT, AND ELIGIBILITY CONFIRMATION

All potential subjects identified through standard clinical practice at the site will be listed on a Screening Log and provided with detailed study information, including a description of TCMS.

We anticipate that 350 patients will be screened and 20 patients will be randomized to either placebo or intervention

If the subject is willing to participate, written informed consent will be obtained.

A subject is considered provisionally enrolled upon completion of the informed consent process.

Subjects provisionally enrolled will be taught how to complete a 7-day diary recording low back pain and will complete this diary before randomization (Self-Report).

Subjects will not be told the pain scores are needed for study inclusion.

The principal investigator or a member of the study team will review the diary to confirm that the subject's mean pain intensity score meets the inclusion criteria. Subjects who do not complete the diary or who fail to meet preliminary pain eligibility requirements will not be randomized, are ineligible for participation in the study and will not be counted in the number of enrolled patients. In such cases, the principal investigator or an authorized designee will log this into the data collection system.

If a patient is unable to tolerate at least 50% of the max 1.2T they will be excluded from the study.

** A significant change for this study is defined as a 20% increase or decrease in dosing of the patient's opioid dose and/or or a change in the medication class (adding or removing other types of medicine used to treat pain).*

*** This exclusion is restricted to opioids, benzodiazepines and psychotropics.*

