18.0 INCLUSION /EXCLUSION CRITERIA

18.1 INCLUSIONS

1. Age \geq 18 years of age
2. Prescription pharmacologic treatment is insufficient for treatment of pain
3. Pain duration of \geq 6 months
4. Pain limits physical activity

5. Pain occurs daily
6. Chronic low back pain, with or without leg pain, associated with MRI or other imaging study consistent with lumbo-sacral spine disease with or without nerve compression
7. Failed back surgery patients without metal implant
8. Pain intensity ≥ 5 at the time of enrollment and a self-reported pain score of ≥ 4 over the 7 preceding days.

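### The one stated between-arm comparison of mean pain is a change score with no baseline adjustment; ANCOVA on the mandatory diary mean would remove chance-imbalance shift and may gain precision

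*Combined protocol and SAP*

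**What the plan says.** Section 12.0 (Effectiveness of Analysis) gives the pain comparison as "Comparison of mean magnitude of treatment effect (change in NPRS) between sham and active treatment (cumulative responder analysis"). It sits under a "Quantitative, but not statistically powered, trend-analysis of effectiveness of active treatment vs. sham". Section 26.0 (Data Analysis) adds "Descriptive statistics, trend analysis of endpoint means for effectiveness". Neither section names a model, covariate, interval or rating time.

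A baseline measure is nonetheless collected. Section 9.2: "Patient will document in a diary the severity of their pain on each day of the preceding week just prior to treatment". Section 17.0 makes it a condition of entry: "Subjects who do not complete the diary or who fail to meet preliminary pain eligibility requirements will not be randomized". Every randomised subject should therefore have a diary mean.

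Which baseline the change is measured from is not stated. Section 11.0 defines treatment success against a mean baseline score, which points to the diary. The study schedule table after Section 26.0 has a row "Day 1 (baseline = start of treatment"), which points to a single rating on the day of treatment.

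Section 16.0 sets the size: "20 (10 control and 10 intervention) subjects who complete treatment/sham based on an estimate that this number will be sufficient". Group Allocation (the first of two sections numbered 20.0) does not stratify by pain.

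**The concern.** With 10 subjects per arm and no stratification on pain, the arms can easily start at different pain levels. Subtracting baseline handles this exactly only if one extra point at baseline predicts one extra point at follow-up. If it does not, part of the chance difference stays in the active-minus-sham estimate, and the estimate may be noisier than the data allow.

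This matters because the success rule in Section 11.0 looks at the active arm alone. Subjects are selected for high pain ("Pain intensity ≥ 5 at the time of enrollment and a self-reported pain score of ≥ 4 over the 7 preceding days"), so regression to the mean and placebo response can lower scores without any device effect. The sham contrast is what separates these from a treatment effect, and the trial is meant to inform a decision on further study.

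**Working it through.** **The plan's own figures.** The documents give no SD, correlation, effect size, alpha or power. The figure of 20 rests on an estimate and cannot be reproduced or called wrong. Everything below uses assumed ranges.

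**Inputs.** From Section 16.0: n = 10 per arm, N = 20. Assumed: correlation rho between baseline and follow-up; ratio s = SD(baseline)/SD(follow-up); a linear relation; normal baseline.

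**Chance imbalance.** The SD of the difference in baseline means is sqrt(2/10) = 0.447 baseline SDs. The probability that it exceeds 0.5 SD in either direction is 2 × [1 - Φ(0.5/0.447)], about 0.26.

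**Residual shift.** Let beta = rho × SD(follow-up)/SD(baseline) = rho/s. For a baseline difference d, the change contrast moves by (beta - 1) × d.
- Equal SDs, d = 0.5 SD: the shift is 0.35, 0.25 and 0.15 SD in size at rho 0.3, 0.5 and 0.7.
- s = 0.5, rho = 0.5: beta = 1 and the shift is zero.
- s = 0.75, rho = 0.8: beta = 1.07, and the change score under-corrects.

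**Variance.**
- Change: (2/n) × (SDb² + SDf² - 2·rho·SDb·SDf)
- ANCOVA: (2/n) × SDf² × (1 - rho²) × (N - 3)/(N - 4), where the last factor is 17/16 = 1.0625
- Ratio, ANCOVA to change: 1.0625 × (1 - rho²)/(s² + 1 - 2·rho·s)

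| s | rho 0.3 | rho 0.5 | rho 0.7 |
|---|---|---|---|
| 1.00 | 0.69 | 0.80 | 0.90 |
| 0.75 | 0.87 | 0.98 | 1.06 |
| 0.50 | 1.02 | 1.06 | 0.99 |

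Example, s = 0.75 and rho = 0.5: 1.0625 × 0.75/(0.5625 + 1 - 0.75) = 0.797/0.8125 = 0.98.

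With equal SDs the ratio reduces to 1.0625 × (1 + rho)/2. It reaches 1 at rho = 2/1.0625 - 1 = 0.88. A simulation of 20,000 trials per value of rho gave 0.69, 0.80, 0.89 and 1.01 at rho 0.3, 0.5, 0.7 and 0.9, in agreement with the formula.

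**Worst case.** The bracket in the change variance equals SDf²(1 - rho²) + (rho·SDf - SDb)², which is never below SDf²(1 - rho²). ANCOVA's penalty therefore cannot exceed 17/16, about 6% of variance. It is reached when beta = 1.

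**In NPRS points** (assumed follow-up SD 1.5, rho 0.5). The ANCOVA SE is 1.5 × sqrt(0.2 × 0.75 × 1.0625) = 0.599, so the 95% half-width is 2.110 × 0.599 = 1.26 in both cases below.
- Equal SDs: change SE 1.5 × sqrt(0.2 × 1) = 0.671, half-width 2.101 × 0.671 = 1.41. Typical shift 0.5 × 1.5 × 0.447 = 0.34.
- s = 0.75: change SE 1.5 × sqrt(0.2 × 0.8125) = 0.605, half-width 1.27. Typical shift (1 - 0.667) × 1.125 × 0.447 = 0.17.

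**The case against.** The strongest reply is that the gain may not exist here. The entry floors cut off low baseline scores, and the diary mean averages seven ratings, while follow-up scores can fall to 0. Both features tend to make the baseline SD the smaller one. At s = 0.75 and rho 0.5 the half-width gain is about 0.01 points, and at rho 0.7 ANCOVA loses slightly. This stands, and it rules out two stronger readings that a reader might infer: that the plan certainly discards precision, and that a change score over-corrects whenever the correlation is below 1. The condition is a slope below 1, and the documents do not give the slope.

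Three further limits also stand.
- The wording names a quantity, not a model. ANCOVA with change as the outcome and baseline as covariate gives the same arm coefficient as ANCOVA on the post-treatment score. The plan is silent on adjustment; it does not reject it.
- This is not the only active-versus-sham estimate. Section 12.0 also lists medication use, non-drug treatment, the Global Pain Scale, satisfaction and unwanted effects.
- Over repeated randomisation the change contrast is unbiased. The shift described here is conditional on the imbalance that happens to occur.

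The reply does not defeat the recommendation. The penalty is capped at about 6% of variance while the gain reaches 31% at rho 0.3 with equal SDs, so rho need not be known to justify specifying ANCOVA.

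**Conclusion.** The point holds as a matter of under-specification with a better method at hand. The stated comparison of mean pain is a change score, no adjustment is specified, and the covariate is already mandatory. ANCOVA removes the shift from chance imbalance under a linear model and changes the variance by between about -31% and +6% over the values examined. These figures rest on assumed correlations and SD ratios. The 6% cap also assumes a normal baseline, which truncation at entry makes approximate.

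The consequence is limited. A reader might infer that the study's success declaration is at risk, but Section 11.0 rests on the active arm (at least 3 of 10) and on related serious adverse events, not on this contrast. The contrast is expressly unpowered and descriptive, and even a half-width of 1.26 points is wide. This is a low-cost improvement to an estimate meant to inform later work, not a flaw that invalidates the trial.

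**What to change.** In Sections 12.0 and 26.0:

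1. Estimate the active-minus-sham difference by ANCOVA of post-treatment NPRS on arm and the 7-day diary mean, with a 95% confidence interval.
2. Name one outcome in advance, for example the mean of ratings from 1 to 48 hours. First reconcile the rating times: 6 hours appears only in the Schedule of Events, 3 hours only in the study schedule table, and neither is in Section 9.4.
3. State that the diary mean, not the Day 1 rating, is the baseline.
4. Keep the cumulative responder curve as a separate descriptive display instead of attaching it to the comparison of means.

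The cost is one degree of freedom and a possible variance loss of up to about 6%. In the worst case the interval is wider by a factor of sqrt(1.0625) × 2.110/2.101, or about 1.035. No new data or subjects are needed. An averaged outcome does need a short rule for missing ratings, so the edit is a few sentences. The study success rule is unchanged.

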13.0 SUBJECT SAFETY

Board-certified anesthesiologists are immediately available.

The risk level to subjects is considered minimal. The device shares technology with an FDA-approved TMS with which no adverse events (AEs) have been associated (<http://www.gpo.gov/fdsys/pkg/FR-2014-07-08/html/2014-15876.htm>).

The “dose” of magnetic stimulation is comparable to that delivered during magnetic resonance imaging (MRI) but is transient and localized to the area of pain. Based upon clinical experience, viz. with MRI, AEs are not anticipated with this application of magnetic stimulation.

